3.1 Eligibility

3.1.1 Case Selection Criteria

- 7-12 years old (grade 1 to grade 6 of primary school);
- Spherical Equivalent ranged from - 0.5D to - 6.0D, astigmatism < 0.75D, binocular diopter gap < 1.0D;
- No ophthalmopathy except ametropia was found.

3.1.2 Exclusion criteria for cases

- has amblyopia, strabismus and other eye diseases.
- Serious allergy to atropine eye drops;
- Atropine eye drops have been used to control myopia.
- Other therapeutic eye drops are being used or have not been discontinued for more than a month.
- There is a contraindication of mydriasis.
- Patients with severe heart, lung, liver, gallbladder and kidney diseases;
- Patients who had to take other drugs because of other diseases affected the results of this test;
- Those who have participated in other clinical trials in the past three months;
- Researchers believe that there are other unsuitable participants.

3.2 Groups and Sample size

Myopic children aged from 7-12 years old are randomly allocated into two groups: combined use of atropine sulfate 1% ophthalmic ointment and atropine sulfate 0.01% eye drop (experimental group) and atropine sulfate 0.01% eye drop (control group). Each group includes 111 participants.

3.3 Medications and usage:

3.3.1 control group: atropine sulfate 0.01% eye drop, once a day, once a drop, for two years;

3.3.2 Combined application group: atropine sulfate 1% ophthalmic ointment, once a day for the first week, once a drop for both eyes; and then once a week, once a drop for both eyes for half a year. Half a year later, atropine sulfate 0.01% eye drop is used once a day, one drop each time, with both eyes for one and a half years. Usage: Drop it into conjunctival sac, about the size of a rice grain, press the nasal root with thumb and index finger for 2 minutes after dripping, and use it before going to bed. Patients once a week are advised to use it before going to bed on Friday night.

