The mechanism of atropine controlling myopia has not been fully elucidated. Early studies suggested that atropine could control myopia by regulating mechanism. However, McBrien found that atropine could still control the development of myopia after cutting off the regulating pathway through animal experiments. Therefore, the mainstream view is that atropine controls myopia by non-regulating mechanism. It may be through the antagonism of Mreceptor signaling pathway on the retina or scleral surface to slow down the development of myopia, but the specific mechanism has not yet been fully elucidated. Atropine eye drops belong to mydriasis and ciliary paralysis drugs. Long-term use of atropine eye drops can lead to symptoms such as dilatation of pupils, photophobia and blurring of close-range objects. These symptoms are closely related to drug concentration and frequency of use.

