3.4.2 Ophthalmology inspection project operation rules

3.4.2.1 Vision test: The eyesight examination used the ETDRS visual acuity chart (LCD backlit lamp, WH0701), the test distance was 4 meters, and the visual target at 20/20 was the same height as the eye of the examinee. The recognition time of each visual target is 2~3s; the eye of the subject is required to be opened normally for examination, and the blinking, yawning, neck stretching and peeking are strictly prevented. Vision is converted to a decimal count record. Visual acuity examination includes two parts: uncorrected visual acuity (UCVA) and corrected visual acuity (CVA). Children who are not wearing glasses are only examined by UCVA, and children who wear glasses are required to check CVA after completing the UCVA test.

3.4.2.2 Intraocular pressure measurement Intraocular pressure was measured using a non-contact tonometer (NT-4000, Nidek, USA). Each eye was repeatedly measured 3 times and averaged, and the difference between each two was less than 5 mmHg. Those with an intraocular pressure higher than 24 mmHg should be recorded and added for visual field examination.

3.4.2.3 Accommodation, near visual acuity: Accommodation is measured using a Royal Air Force (RAF) near point rule (Harlow, Essex, UK) with best-corrected distance spectacle correction. Near visual acuity is assessed using best-corrected distance spectacle correction with a reduced logMAR reading chart placed at 40 cm under well-lit conditions

3.4.2.4 Mesopic pupil size: measured by automated computer refractometer (KR-8900, Topcon, Japan) after staying in a dark room for 5 minutes at least. At least 5 pupil size readings were recorded and averaged.

3.4.2.5 Ophthalmologist examination Ophthalmologist examinations included anterior segment slit lamp examination (66 Vision. Tech, Suzhou, China) and ophthalmoscopy examination(66 Vision. Tech, Suzhou, China). To exclude those children with cycloplegia contradictions.

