3.4.2.12 Wide angle OCT/OCTA (Zeiss-9000) Wide-angle OCT/OCTA examinations were performed after cycloplegia. OCT/OCTA location: macular + optic disc area. Shooting mode: 12*12mm, 15*9mm angio mode; 16mm loop sweep mode (horizontal and vertical directions) a total of 8 scans. Shooting requirements: communicate more with the subject; the forehead and chin must be close to the instrument. If the image quality is affected by blinking or eye movement during shooting, participants need to re-shoot. This item is optional for children under 6 years old.

3.4.3 Questionnaire: The questionnaire is about the time children spend on outdoor activities and near work.

4. Follow up

4.1 Frequency: Combined use of 1% atropine and 0.01% atropine group is followed up after first week, then every three months. 0.01% atropine group is followed up every three months.

4.2 Examinations:

4.2.1 First week follow up for combined use group: accommodation, near vision acuity > mesopic pupil size > Autorefraction and subjective refraction > IOL-Master, Pentacam, Swept-source optical coherence tomography (SS-OCT, Topcon), wide-angle optical coherence tomography angiography(OCTA,Zeiss-9000)

4.2.2 Every three months: accommodation, near vision acuity > mesopic pupil size > slit lamp anterior segment examination > cycloplegia > Autorefraction and subjective refraction > IOL-Master, Pentacam, Swept-source optical coherence tomography (SS-OCT, Topcon), wide-angle optical coherence tomography angiography(OCTA,Zeiss-9000)

5. Statistical Analysis

5.1 Descriptive statistics A. Continuity variables: sample size, mean, standard deviation, minimum, maximum, quartile B. Classification variable or grade variable: frequency distribution

5.2 statistical methods A. Continuous variables: The normality test uses the Kolmogorov-Smirnov test. If the normal distribution is satisfied, the t test or one-way ANOVA is used; if the normal distribution is not satisfied, the Mann-Whitney U test or the Kruskal Wallis test is used. The two-two comparison between groups was performed using the Bonferroni method. B. Categorical variable: chi-square test. C. Correlation analysis:

simple linear regression and stepwise multiple linear regression, using nonlinear regression if necessary.

5.3 Statistical significance All differences were statistically defined as $P < 0.05$ (bilateral)

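### In the weekly 1% phase, the month-3 and month-6 pupil, accommodation and near-acuity readings have no days-since-dose rule, and the protocol makes no provision to record the last dose

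*Combined protocol and SAP*

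**What the plan says.** Section 3.3.2 gives the combined arm 1% ointment daily for a week, "and then once a week, once a drop for both eyes for half a year". On the dosing day it says only: "Patients once a week are advised to use it before going to bed on Friday night". Section 3.3.1 gives controls "atropine sulfate 0.01% eye drop, once a day, once a drop, for two years".

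On visits, section 4.1 says: "Combined use of 1% atropine and 0.01% atropine group is followed up after first week, then every three months". Controls are also seen quarterly. Neither arm has a visit weekday, a visit window or a required interval from the last dose.

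The order of examinations is in section 4.2.2: "4.2.2 Every three months: accommodation, near vision acuity > mesopic pupil size > slit lamp anterior segment examination > cycloplegia". Accommodation, near acuity and mesopic pupil size are therefore read before cyclopentolate is given. The pupil rule in section 3.4.2.4 fixes the conditions of the reading ("after staying in a dark room for 5 minutes at least. At least 5 pupil size readings were recorded and averaged"), and section 3.4.2.3 fixes the instrument, correction and viewing conditions for accommodation and near acuity. Neither mentions time since dose. The examination lists in sections 3.4.1 and 4.2 contain no dosing item, and the questionnaire in section 3.4.3 covers outdoor time and near work only.

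**The concern.** Removing adverse effects is part of the first objective in section 2. Section 1.3 names pupil dilatation, photophobia and near blur as effects of atropine and adds: "These symptoms are closely related to drug concentration and frequency of use". If these effects fade between weekly doses, a reading in the combined arm depends on where in the week the appointment falls. A control child dosed daily has no comparable cycle.

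The between-arm tolerability comparison for the weekly regimen rests on months 3 and 6. The week-1 visit (section 4.2.1) has no control counterpart and follows daily dosing. Section 5.2 plans t tests or Mann-Whitney tests for continuous measures, with no term for days since dose. The reported contrast could therefore partly reflect how appointments were booked.

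**Working it through.** The plan states no figure on this point, so there is none to reproduce. The check is a reading of the schedule followed by an illustration.

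**Visits affected.** Quarterly visits over 24 months number 24 / 3 = 8: months 3, 6, 9, 12, 15, 18, 21 and 24. Only months 3 and 6 fall in, or at the end of, the weekly phase. The documents do not say whether the month-6 visit comes before or after the switch to 0.01%, so the count is one or two of eight, in one arm.

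**Possible interval since dose.** Assume a Friday dose at 21:00 and a visit at 10:00 (both times are assumptions). A Saturday visit is 13 / 24 = 0.54 days after the dose, and each later weekday adds one day: Monday 2.54, next Friday 6.54. The range is about 0.5 to 6.5 days, or about 2.5 to 6.5 days for a Monday-to-Friday clinic. This supposes every child follows the Friday advice; departures from it would make the true interval less certain.

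**Residual effect.** The documents give no decay rate. Assume a residual fraction of 0.5^(d/h), with d in days and h the half-life in days. The Saturday-to-Friday ratio is then 2^(6/h) and the Monday-to-Friday ratio is 2^(4/h). For h = 2, these are 2^3 = 8.0 and 2^2 = 4.0.

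| Assumed h (days) | Saturday | Monday | Next Friday | Sat/Fri ratio | Mon/Fri ratio |
|---|---|---|---|---|---|
| 2 | 0.83 | 0.41 | 0.10 | 8.0 | 4.0 |
| 4 | 0.91 | 0.64 | 0.32 | 2.83 | 2.0 |
| 7 | 0.95 | 0.78 | 0.52 | 1.81 | 1.49 |
| 14 | 0.97 | 0.88 | 0.72 | 1.35 | 1.22 |

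**From single readings to arm means.** The ratios compare one child on one day with another child on another day. If visits are spread evenly over seven days, the mean residual is 0.37, 0.57, 0.72 and 0.84 for the four half-lives, with a between-day SD of 0.24, 0.20, 0.14 and 0.08. That is added variance, in the combined arm only.

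If all visits fall evenly on Monday to Friday, the means become 0.23, 0.47, 0.64 and 0.80. For h = 4, for example, (0.64 + 0.54 + 0.46 + 0.38 + 0.32) / 5 = 0.47. Clustering of this kind lowers the arm mean relative to the whole-week average, by a factor of 0.47 / 0.57 = 0.82 at h = 4 and 0.80 / 0.84 = 0.95 at h = 14. These shifts are much smaller than the individual extremes.

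**The case against.** The strongest reply is that an arm mean over children seen on different days is a fair description of a week on treatment, so the harm is mostly noise. That stands if visit days are spread. Bias needs clustering, and the documents give no clinic days. The size also has no source: section 1.3 ties symptoms to concentration and frequency and says nothing about decay by day, and proportionality between residual fraction and pupil or accommodation change is a further assumption. That stands too.

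Four stronger readings are tempting, and the documents do not support them.

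- A reader might infer that refraction is distorted by weekday as well. At quarterly visits refraction follows cyclopentolate, with light reflection and pupil diameter checked (sections 3.4.2.6 and 4.2.2). The point is confined to the measures taken before cycloplegia.
- A reader might infer that nothing could be done afterwards. The advised Friday and the visit date give an approximate interval. It is only approximate, because Friday is advised and not required.
- A reader might take it as fact that the last dose goes unrecorded. The documents show only that the protocol makes no provision for it. Section 3.4.1 calls its list brief, and the case report forms are not available.
- A reader might infer that the trial could report a several-fold different side effect. That would require nearly all children to be seen at one end of the week, and a short half-life.

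The week-1 visit does give a within-arm change from baseline, but after daily dosing and without a control reading, so it does not replace months 3 and 6.

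**Conclusion.** The point holds in a narrow form. As written, the plan leaves the month-3 and month-6 readings of pupil size, accommodation and near acuity in the combined arm free to fall anywhere from about 0.5 to 6.5 days after a weekly dose, and does not provide for knowing which. The consequence is extra variance in one arm and, if visit days cluster, a biased tolerability contrast: understated relative to the weekly average if visits fall late in the dosing week, overstated if early.

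That these readings vary with days since dose is a pharmacological inference which section 1.3 supports only indirectly, and its size is unknown. The range of 8.0 down to 1.35 rests on assumed half-lives of 2 to 14 days, exponential decay and full adherence to Friday dosing. This is a low-severity point, worth acting on because the remedy is nearly free.

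**What to change.** Leave dosing unchanged.

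1. Record product, date and time of the last dose at every visit in both arms. The product entry also shows whether a month-6 reading was taken on 1% or after the switch.
2. Report the distribution of days since dose at months 3 and 6 in the combined arm. A table of outcomes by single day would be thin: 111 / 7 is about 16 children per day.
3. Give the between-arm contrast for pupil size, accommodation and near acuity at those visits with days since dose as a covariate, or at a stated interval. Because controls dose daily, the term should apply within the combined arm and be centred at the stated interval, so that the arm coefficient is the contrast at that point.
4. Where practical, book the two visits in a common days-since-dose window.

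The cost is one form entry, one short table and one model term. The downside of the window is a minor booking constraint at two visits, and readings that describe only that part of the dosing week. Items 1 to 3 do not depend on it.

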3.4 Examination

3.4.1. Examination process: The brief process is as follows: Identity information registration > height, weight > naked eye vision & wearing vision > intraocular pressure > accommodation, near vision acuity > mesopic pupil size > slit lamp anterior segment

examination > cycloplegia > Autorefractometry and subjective refraction > IOL-Master, Pentacam, Swept-source optical coherence tomography (SS-OCT, Topcon), wide-angle optical coherence tomography angiography(OCTA, Zeiss-9000)> fill out the questionnaire.

3.4.2 Ophthalmology inspection project operation rules

3.4.2.1 Vision test: The eyesight examination used the ETDRS visual acuity chart (LCD backlit lamp, WH0701), the test distance was 4 meters, and the visual target at 20/20 was the same height as the eye of the examinee. The recognition time of each visual target is 2~3s; the eye of the subject is required to be opened normally for examination, and the blinking, yawning, neck stretching and peeking are strictly prevented. Vision is converted to a decimal count record. Visual acuity examination includes two parts: uncorrected visual acuity (UCVA) and corrected visual acuity (CVA). Children who are not wearing glasses are only examined by UCVA, and children who wear glasses are required to check CVA after completing the UCVA test.

3.4.2.2 Intraocular pressure measurement Intraocular pressure was measured using a non-contact tonometer (NT-4000, Nidek, USA). Each eye was repeatedly measured 3 times and averaged, and the difference between each two was less than 5 mmHg. Those with an intraocular pressure higher than 24 mmHg should be recorded and added for visual field examination.

3.4.2.3 Accommodation, near visual acuity: Accommodation is measured using a Royal Air Force (RAF) near point rule (Harlow, Essex, UK) with best-corrected distance spectacle correction. Near visual acuity is assessed using best-corrected distance spectacle correction with a reduced logMAR reading chart placed at 40 cm under well-lit conditions

3.4.2.4 Mesopic pupil size: measured by automated computer refractometer (KR-8900, Topcon, Japan) after staying in a dark room for 5 minutes at least. At least 5 pupil size readings were recorded and averaged.

3.4.2.5 Ophthalmologist examination Ophthalmologist examinations included anterior segment slit lamp examination (66 Vision. Tech, Suzhou, China) and ophthalmoscopy examination(66 Vision. Tech, Suzhou, China). To exclude those children with cycloplegia contradictions.

3.4.2.6 Cycloplegia The cycloplegia procedure is as follows: 1 drop of 0.5% proparacaine (Alcaine, Alcon) is added to the conjunctival sac of each eye, and 1 drop of 1% cyclopentolate is added to each eye after 15 seconds. (Cyclogyl, Alcon), 5 minutes apart. After each drip, ask the participant to press the inner canthus for a few seconds gently and try to take the head back posture. The last drop of cyclopentolate was instilled into the conjunctival sac for 30 minutes to check for light reflection. If the light reflection disappeared and the pupil diameter was greater than 6 mm, cycloplegia was considered complete. If the light reflection still exists, add a third drop of cyclopentolate, and re-

examine the light reflection and pupil diameter after 20 minutes. If there was still light reflection, the inspector needs to record this. During cycloplegia, if the participant has symptoms of ocular discomfort, the ophthalmologist should carefully examine it and give an appropriate treatment.

3.4.2.7 Axis measurement: The axial measurement was performed using an IOL Master (version 5.02, Carl Zeiss Meditec, Germany). Simulated eye calibration was needed before measurement. Each eye was measured repeatedly for 3 times, and the difference was less than 0.02 mm each time. For those who still have large fluctuations in multiple measurements, the examiner needs to record it.

3.4.2.8 Measurement of refractive state and corneal radius of curvature (CR) The refractive status and CR measurements were performed using an automated computer refractometer (KR-8900, Topcon, Japan), which was performed after ciliary muscle paralysis. Simulated eye calibration needed before measurement. Each eye was repeatedly measured three times to average, and if any two results differ by more than 0.5 D, the measurement needed to be repeated. If there were still significant differences in the results of multiple measurements, the examiner needed to record it.

3.4.2.9 Subjective optometry Children who do not wear glasses have a UCVA of less than 0.8 (less than 0.63 for children 6 years of age and younger) or children with glasses have a CVA of less than 0.8 (children under 6 years of age and below 0.63) need to finish a subjective optometry after cycloplegia in order to measure the best corrected visual acuity (BCVA). If the BCVA is less than 0.8 (less than 0.63 for children aged 6 and under), or the degree of compliance during the examination is poor, the examiner should record it. If the BCVA is less than 0.8 (children under 6 years of age and below is less than 0.63), further examination by an ophthalmologist is required to determine whether the inclusion conditions are still met.

3.4.2.10 Pentacam (OCULUS Optikgeratic GmbH, Germany) was examined after cycloplegia. Measurements include corneal diameter and curvature, anterior chamber depth and volume, anterior chamber angle, pupil diameter, crystal thickness, etc. Shooting requirements: Image quality display "OK", crystal thickness value is available. This item is optional for children under 6 years old.

3.4.2.11 SS-OCT (Topcon) SS-OCT (DRI OCT Triton, Topcon, Tokyo, Japan) was examined after cycloplegia. OCT location: Macular + optic disc area. Shooting mode: 12*9 mm 3D scan mode (4 overlap) / Line scan (64 overlap) + 9 mm radial scan mode (16 overlap, follow up mode) + optic disc area 9 Mm radial scan mode (16 overlap, follow up mode) + macular area 7*7 mm 3D scan mode (4 overlap) + optic disc area 6*6 mm 3D scan mode (4 overlap). Shooting requirements: input spherical error, cylinder, axis length, corneal curvature radius correction magnification before shooting; image signal of strength 3D scan mode is not less than 50, radial scan mode is not lower than 60, peripheral image avoids mirror flip as much as possible. When shooting the disc area, we need to manually adjust the shooting center to the center of the disc. If the image quality is affected by blinking or eye movement during shooting, participants need to re-shoot. If

participants still can't meet the requirements, participants need to record it. SS-OCT comes with a fundus color photograph. The shooting position is required to be consistent with the SS-OCT scanning position and to avoid eyelids, eyelashes and hair occlusion. Dark areas are avoided in the image, and the image quality is not less than 90. This item is optional for children under 6 years old.

3.4.2.12 Wide angle OCT/OCTA (Zeiss-9000) Wide-angle OCT/OCTA examinations were performed after cycloplegia. OCT/OCTA location: macular + optic disc area. Shooting mode: 12*12mm, 15*9mm angio mode; 16mm loop sweep mode (horizontal and vertical directions) a total of 8 scans. Shooting requirements: communicate more with the subject; the forehead and chin must be close to the instrument. If the image quality is affected by blinking or eye movement during shooting, participants need to re-shoot. This item is optional for children under 6 years old.

3.4.3 Questionnaire: The questionnaire is about the time children spend on outdoor activities and near work.

4. Follow up

4.1 Frequency: Combined use of 1% atropine and 0.01% atropine group is followed up after first week, then every three months. 0.01% atropine group is followed up every three months.

4.2 Examinations:

4.2.1 First week follow up for combined use group: accommodation, near vision acuity > mesopic pupil size > Autorefraction and subjective refraction > IOL-Master, Pentacam, Swept-source optical coherence tomography (SS-OCT, Topcon), wide-angle optical coherence tomography angiography(OCTA,Zeiss-9000)

4.2.2 Every three months: accommodation, near vision acuity > mesopic pupil size > slit lamp anterior segment examination > cycloplegia > Autorefraction and subjective refraction > IOL-Master, Pentacam, Swept-source optical coherence tomography (SS-OCT, Topcon), wide-angle optical coherence tomography angiography(OCTA,Zeiss-9000)

5. Statistical Analysis

5.1 Descriptive statistics A. Continuity variables: sample size, mean, standard deviation, minimum, maximum, quartile B. Classification variable or grade variable: frequency distribution

5.2 statistical methods A. Continuous variables: The normality test uses the Kolmogorov-Smirnov test. If the normal distribution is satisfied, the t test or one-way ANOVA is used; if the normal distribution is not satisfied, the Mann-Whitney U test or the Kruskal Wallis test is used. The two-two comparison between groups was performed using the Bonferroni method. B. Categorical variable: chi-square test. C. Correlation analysis:

simple linear regression and stepwise multiple linear regression, using nonlinear regression if necessary.

5.3 Statistical significance All differences were statistically defined as $P < 0.05$ (bilateral)

5.4 Subgroup analysis Subjects will be assigned to different subgroups for subgroup analysis based on age, gender, diopter, axial length, fundus structure, and functional changes.

5.5 Interim analysis Baseline data (2019) and follow-up data are used for analysis and reporting.

6. Ethical issues

6.1 Ethics committee The study will be carried out after the approval of the Shanghai General Hospital Ethics Committee and strictly abide by the Helsinki Declaration.

6.2 Protect the privacy of participants In order to protect the privacy of the children and adolescents in the test, when the research materials are provided to other organizations, the subject code or initials should be used instead of their ID number or real name. In addition, the researcher and the relevant staff involved in the research must keep the privacy information of the children and adolescents in the test confidential.

6.3 Informed consent The informed consent form will be distributed to the children and adolescents participating in the study and their parents or guardians after approval by the ethics committee. For children and adolescents and their parents or guardians who voluntarily agree to participate in the study, parents or guardians are required to sign an informed consent form prior to the baseline study. Before signing the informed consent form, the researcher should fully introduce the content of the study, the benefit of the subject and the potential risks, and confirm that the children and adolescents and their parents or guardians fully understand and voluntarily sign the informed consent form. When signing the informed consent form, the parent or guardian has sufficient time to consider and has the right to ask questions. For questions from parents or guardians, the researcher needs to provide adequate answers. For parents or guardians who agree to sign an informed consent form, the investigator signs the informed consent form after the informed consent is fully explained and states the relationship with the child and adolescent. Informed consent is in duplicate, one of which is kept by the parent or guardian and the other is kept by the researcher. During the research process, if there is a major change in the research content, the revised informed consent form should be sent to the ethics committee for approval. After the approval, the researcher must fully communicate with the children and adolescents and their parents or guardians, and confirm that they agree to continue to participate in the study and re-sign the informed consent form.

7. Funds and insurance funds

Before the start of the study, funds were raised by the Shanghai Eye Disease Prevention and Treatment Center.

8. References

- [1] impairment: 2010. *Br J Ophthalmol*. 2012 ;96:614-8.

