1.3 Studies about atropine for controlling myopia progression

In order to reduce the incidence of high myopia, many myopia control interventions have been carried out in children and adolescents at home and abroad. Among them, atropine, an M-receptor antagonist, has been shown to be effective in myopia control in many experimental and clinical trials in recent years. In ATOM2 study in Singapore, a randomized controlled clinical trial was conducted. Two years after the use of 1% atropine eye drops, children's myopia decreased by 0.92D and eye axis increased by 0.4mm compared with the control group. After 2 years of treatment with 0.5%, 0.1% and 0.01% respectively, the myopia of children increased by 0.30D, 0.38D and 0.49D, respectively, which were

significantly lower than that of the control group (1.20D). Although 1% atropine eye drops had myopic rebound effect after discontinuation, the rebound effect disappeared when the concentration of atropine was reduced to 0.1% and 0.01%.

In the LAMP study in Hong Kong, after one year of treatment with 0.05%, 0.025% and 0.01% respectively, the myopia of children increased by 0.27D, 0.46D and 0.59D, which were significantly lower than that of the control group (0.81D), and the ocular axis increased by 0.20mm, 0.29mm and 0.36mm, respectively, which were lower than that of the control group (0.41mm). Similar studies at home and abroad have also confirmed that the use of low-concentration atropine has a good effect on myopia control. At present, in Taiwan, Hong Kong, Singapore and other Chinese areas, children with high myopia risk and rapid growth of myopia have been more commonly treated with low-concentration atropine eye drops for intervention.

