1.4 The objectives of our study

From previous studies, investigators can find that 1% atropine has good effect in early myopia control, but its side effects are great, long-term use compliance is poor, and there is a rebound effect; 0.01% atropine has poor effect in early myopia control, and the effect of follow-up for one year is not as good as 0.05%, but the effect of follow-up for two years is equal to 1%, that is, long-term use effect is good, and there are few side effects. Considering that only 1% or 0.01% atropine eyedrops (gels) are available in atropine eyedrops approved by the drug administration, investigators consider whether 1% atropine can be used for six months, and 0.01% atropine for one and a half years to achieve better early myopia control, late consolidation efficacy and side effects. In addition, the current clinical studies mainly focus on diopter and ocular axis. This project will explore the changes of lens and fundus after atropine treatment, whether there are indicators that reflect the effect of atropine control earlier and more accurately than diopter and ocular axis, and explore the target of atropine for myopia control.

2. Research Objectives

To explore a better way to control myopia progression and eliminate adverse effects at the same time;

To provide reliably evidence for clinical guideline of atropine use in children;

To investigate the mechanism of atropine on eyes.

3.Trail Design

a randomized controlled, prospective cohort study, no mask.

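### Magnification correction is required for SS-OCT (3.4.2.11) but not for wide-angle OCT/OCTA (3.4.2.12), so transverse OCTA measures can drift with axial growth unless scale is corrected elsewhere

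*Combined protocol and SAP*

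**What the plan says.** Section 3.4.2.11 (SS-OCT) tells the operator to "input spherical error, cylinder, axis length, corneal curvature radius correction magnification before shooting". Section 3.4.2.12 (wide-angle OCT/OCTA) has no equivalent. It fixes the fields, "Shooting mode: 12*12mm, 15*9mm angio mode; 16mm loop sweep mode (horizontal and vertical directions) a total of 8 scans", and its acquisition rule reads "Shooting requirements: communicate more with the subject; the forehead and chin must be close to the instrument", followed by re-shooting for blinks or eye movement.

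Section 5 mentions neither post-hoc scaling nor adjustment of imaging outcomes for axial length. It plans t tests or rank tests between groups, and simple and stepwise linear regression for correlations. Axial length appears there only as a subgroup variable (5.4).

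Section 1.4 gives the images a purpose: "This project will explore the changes of lens and fundus after atropine treatment", and the trial will ask "whether there are indicators that reflect the effect of atropine control earlier and more accurately than diopter and ocular axis". Section 4.2 schedules "IOL-Master, Pentacam, Swept-source optical coherence tomography (SS-OCT, Topcon), wide-angle optical coherence tomography angiography(OCTA,Zeiss-9000" together at each three-monthly visit, so axial length is available whenever OCTA is done.

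**The concern.** The plan treats biometric correction as necessary for one retinal device and is silent for the other, in the same children at the same visits.

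A scan of fixed angular width covers more retina in a longer eye. If its millimetre scale is not corrected, an unchanged structure reads shorter and smaller as the eye grows, and a region of fixed nominal size samples a different patch of retina. Randomisation does not protect the arm comparison, because the distortion follows axial growth after randomisation and treatment is meant to change that growth.

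Two results would be at risk. An arm difference in an OCTA length or area could be reported as an effect on the retinal circulation when it reflects optics. A correlation between change in such a measure and change in axial length would be partly built in, which weakens the search for indicators.

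**Working it through.** The plan states no figure on OCTA scaling, so there is none to reproduce. The check compares the two sections, as set out above, and then sizes the possible distortion in an area measure.

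**Inputs from the documents**
- One-year axial growth in the Hong Kong study described in section 1.3, for 0.05%, 0.025% and 0.01%: "the ocular axis increased by 0.20mm, 0.29mm and 0.36mm, respectively, which were lower than that of the control group (0.41mm").
- 111 participants per group (3.2), two-sided 0.05 (5.3), two years of treatment (3.3).

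**Assumptions not in the documents**
- Retinal scale is proportional to axial length minus 1.82 mm (Bennett formula).
- Baseline axial length is 24.5 mm.
- Neither the device nor later processing corrects scale.
- Growth in year two equals growth in year one: 2 × 0.36 = 0.72 mm, 2 × 0.29 = 0.58 mm and 2 × 0.20 = 0.40 mm. The last two are stand-ins for a slower-growing arm, since neither 0.05% nor 0.025% is given in this trial.

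**Within-eye shift.** For growth d, the apparent area of an unchanged structure is multiplied by [(24.5 − 1.82)/(24.5 + d − 1.82)]².
- d = 0.72: (22.68/23.40)² = 0.939, so the area reads 6.1% smaller.
- d = 0.58: (22.68/23.26)² = 0.951, so 4.9% smaller.
- d = 0.40: (22.68/23.08)² = 0.966, so 3.4% smaller.

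**Spurious arm gap**
- 0.72 against 0.40 mm: 6.06 − 3.44 = 2.6 percentage points.
- 0.72 against 0.58 mm: 6.06 − 4.92 = 1.1 points.

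**Sensitivity**
- With a baseline of 23.5 or 25.5 mm, the arm gaps move by about 0.1 point (2.7 or 2.5; 1.2 or 1.1). The within-eye shifts move by up to about 0.3 (0.72 mm gives 6.3% or 5.8%).
- With scale simply proportional to axial length, 0.72 and 0.40 mm give 5.6% and 3.2%, a gap of 2.4 points.

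**Chance of a false significant arm difference.** The standard error is SD × √(2/111), where SD is that of the percentage change. The plan gives no SD, so a range is shown (standard errors 0.67, 1.34 and 2.68 for SD 5, 10 and 20).
- Gap 2.6 points: about 97%, 50% and 16%.
- Gap 1.1 points: about 39%, 13% and 7%.

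**Built-in correlation.** Assume an SD of 0.2 mm for axial change and, for simplicity, scale proportional to axial length. The induced SD in area is 100 × 2 × 0.2/24.5 = 1.63%. Then r = −1.63/√(1.63² + e²), where e is the SD of unrelated variation. For e = 5, 10 and 20%, r = −0.31, −0.16 and −0.08.

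**Early visits.** At three months, growth of 0.36/4 = 0.09 mm shifts area by 0.8%. Against 0.20/4 = 0.05 mm (0.4%), the arm gap is about 0.35 points.

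**The case against.** The strongest reply is that silence is not absence. The documents do not say how the second device or its export handles scale, so a reader who infers that this trial's OCTA values are uncorrected goes further than the text allows. That stands: the fault is an unspecified requirement, and the consequence is conditional.

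Second, the plan names no OCTA metric. The percentages above are for areas. Layer thickness does not scale this way, and a dimensionless vessel density is affected only through the shift in the region sampled, which is not sized here. That stands too, so the figures cannot be read as applying to OCTA measures in general.

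Third, the growth scenario is borrowed. Both arms use 0.01% for the last 18 of 24 months (3.3), and the experimental arm's growth is unknown. Section 1.3 also reports "eye axis increased by 0.4mm compared with the control group" after two years of 1%, but the experimental arm has 1% for half a year only. The gaps show scale and are not forecasts.

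Fourth, it is tempting to cite the contrast between children: at 23 and 26 mm the area scale differs by about 30%, since (24.18/21.18)² = 1.30. A reader might take this as bias between arms. It is not, because randomisation balances it in expectation and within-eye change largely removes it.

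Fifth, a distortion driven by axial length cannot precede axial length, so the claim of an earlier indicator is less exposed than late correlational claims. The three-month figures agree.

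What the reply does not answer is the difference between two adjacent sections of one protocol, with nothing in section 5 to make it good.

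**Conclusion.** The point holds in conditional form. Followed as written, the plan does not ensure that transverse OCTA lengths, areas and fixed-millimetre regions are free of axial growth, although it does ensure this for SS-OCT. If no correction happens elsewhere, the distortion in an area is about 3% to 6% within eyes over two years and about 1 to 2.6 points between arms, under the assumed scale, baseline and growth. With noisy metrics (SD 10% to 20%), the false-positive rate at the smaller gap is only modestly above 5%. With precise metrics it is large.

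The documents do not support the stronger inference that any OCTA difference found will be an artefact, or that refraction and axial length results are compromised. Those two outcomes are untouched. The weakness lies in the fundus and indicator aims of section 1.4. It merits a change because the plan departs from its own standard and the biometry needed is already collected.

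**What to change.** Add to 3.4.2.12 the correction that 3.4.2.11 already requires: same-visit sphere, cylinder, axial length and corneal radius, entered at capture or applied by an equivalent scaling at export. Use one method for both devices. Scaling by axial length alone would not be the same requirement and could leave the two devices on different scales. If the device or the processing already corrects, say so and name the inputs.

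Add to section 5 that transverse OCTA lengths, areas and regions of interest are compared between arms and used in the indicator search only after this correction.

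The cost is a few sentences and a small processing step, with no extra visit or examination. Refraction and axial length are measured at the same three-monthly visits, and corneal radius comes from the same autorefractor (3.4.2.8). Scans already acquired can be rescaled at export. The downside is slight cropping of fixed-size regions in some eyes.
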